## **Quality assurance**

The TMG will hold meetings every 3-4 months or more as required. Face-to-face meetings where possible will be accompanied by teleconferencing via Zoom and Google hang out.

## Study Dissemination

In addition to local meetings for local collaborators, we plan to submit for presentations to ASGBI, ACPGBI, ASCRS, Tripartite 2020.

The following are all potential papers and are subject to change.

Paper 1. Protocol Paper.

Paper 2: Characterisation and short-term outcomes of the NOLAP Patient in the U.K.

**Paper 3:** Decision-making in the NoLap population.

**Paper 4:** Long-term outcomes for the NOLAP patient in the U.K.

**Paper 5:** Comparison of Pre-operative Prognostic Markers in NoLAP versus ELAP UK Patients.

# Appendix A. Decision-making Options for NoLAP.

Must select at least one of these factors as the MAIN influencing factor.

Patient Factors	Yes/	Surgical Factors	Yes/
	No		No
Patient does not wish to have surgery (Drop down menu of reasons if selecting 'yes': chronic pain, management of stoma, does not want to lose independence i.e. institutionalisation, other – free text)		Poor Pre-op Fitness (Drop-down menu options if selecting 'yes': home oxygen; nursing home resident; bed bound; housebound; advanced comorbidity; other – free text)	
Has Living will in place		Poor prognostic pathology (Drop-down menu options if selecting 'yes': global ischaemia, advanced malignancy; other –free text)	
Patient involved in decision (Drop-down options if selecting 'no': Reduced GCS; severe dementia; acute delirium; power of attorney in place; other – free text)		
 
High prognostic score
 
(Drop-down menu options if selecting 'yes': high NELA score; high frailty score; high P-Possum score, high SORT score)
 
If frailty score used: define which score
 
If yes selected for any score, record actual value (frailty score value or predicted mortality value)
 
	
Anyone else representing the patient involved in the decision (Drop down options if selecting 'yes': next of kin, legal guardian, friend, other)		Surgeon involved in decision (Drop-down menu if selecting 'yes': consultant, associate specialist, staff grade, registrar, core trainee)	

Anaesthetic Factors	Yes/	Intensive Care Factors	Yes/
	No		No
Poor Pre-op Fitness		Poor Pre-op Fitness	
(Drop-down menu options: home oxygen; nursing home resident; bed bound; housebound; advanced comorbidity; other – free text)		(Drop-down menu options: home oxygen; nursing home resident; bed bound; housebound; advanced comorbidity; other – free text)	
Poor prognostic pathology		Poor prognostic pathology	
(Drop-down menu options: global		(Drop-down menu options: global ischaemia,	

ischaemia, advanced malignancy; other –		advanced malignancy; other -free text)	
free text)			
,			
High prognostic score		High prognostic score	
(Drop down many options if colocting was'		(Drop down many options if colocting (yes), high	
(Drop-down menu options if selecting 'yes':		(Drop-down menu options if selecting 'yes': high	
high NELA score; high frailty score; high P-		NELA score; high P-Possum score; high SORT score;	
Possum score; high SORT score)		high frailty score)	
If frailty score used: which score		If frailty score used: which score	
If yes selected for any score, record actual		If yes selected for any score, record actual value	
value (frailty score value or predicted		(frailty score value or predicted mortality value)	
mortality value)			
Unlikely to be weaned from ventilator		Unlikely to be weaned from ventilator	
(Drop down, reasons for this concern)		(Drop-down – reasons for this concern)	
(Drop-down – reasons for this concern)		(Drop-down – reasons for this concern)	
Anaesthetist involved in decision		Intensivist involved in decision	
(Drop-down menu if selecting 'yes':		(Drop-down menu if selecting 'yes': consultant,	
consultant, associate specialist, staff grade,		associate specialist, staff grade, registrar, core	
registrar, core trainee)		trainee)	
Other Specialities	Voc/No	Other factors	
Other Specialities	Yes/No	other factors	
Were any other specialities involved in this		DNACPR in place?	
decision-making process?			
(Drop-down menu options: palliative care;			
geriatrics; accident and emergency;			
medicine; other –free text)			
(For all where 'yes' is answered: Drop-down		Any other factors which influenced the decision (free	
menu to specify most senior grade of additional speciality involved in decision)		text)	

# Appendix B: Proforma

Q1	Study ID	
Q2	Age at admission to study (years)	
Q3	Sex	Male Female
Q4	Comorbidities	CCF Y/N COPD Y/N
		CVA Y/N Dementia Y/N
		Hemiplegia Y/N CKD Y/N
		Leukaemia Y/N DM(complicated) Y/N
		Lymphoma Y/N DM(uncomplicated)
		Y/N
		Mild liver disease Y/N IHD Y/N
		Severe liver disease Y/N PVD Y/N
		Solid tumour Y/N Metastatic tumour
		Y/N
		AIDS Y/N
		Other:
Q5	Polypharmacy (≥5 medications)	Yes No
Q6	Place of Surgical review (choose	Emergency Department
	most relevant)	General Surgical Ward
		Other Surgical ward
		Orthopaedics
		Geriatric ward
		Acute medical ward
		Other medical ward
Q7	Care level prior to admission	Home (no carers)
		Home (with carers)
		Residential Home
		Nursing home
		Intermediate care

		Other:
Q8	Frailty score	1,2,3,4,5,6,7
Q9	NELA score	%
Q10	Interval between admission and	
	laparotomy (days)	
Q11a	Pre-decision Creatinine	
Q11b	Pre-decision CRP	
Q11c	Pre-decision WCC	
Q11d	Pre-decision Lactate	
	(all within 8 hours of decision)	
Q11	Pre-operative clinical diagnosis	
Q12	CT performed pre-operatively	Yes/ no
	(within 24 hours of decision)	
Q13	CT diagnosis	
Q14	Psoas muscle mass (TPI)	
	[TPA/ height)	
Q15	ELAP?	Yes/ no
Q16	Day of decision	Monday to Thursday
		Friday to sunday
Q17	Time of decision (24 hour)	:
Q18	Operation performed at	
	laparotomy	
Q19	Length of stay post-operative or	
	NOLAP decision (days)	
Q20	Length of critical care stay (ICU and	
	HDU) (days)	
L	l	

Q21a	Post-operative complication within 30 days	Yes	No
Q21b	Grade of complication		
Q22	Care level on discharge	Home (no carers)	
		Home (with carers)	
		Residential Home	
		Nursing home	
		Intermediate care	
		Other:	
Q23	30 day mortality	Yes	No
Q24	30 day re-admission	Yes	No
Q25	90 day mortality	Yes	No
Q26	1 year mortality	Yes	No

## **Definitions**

**Q4.** These are comorbidities as defined by the Charlson Comorbidity Index. Each should be marked as present if there is any previous documented history of each diagnosis.

History of medically documented myocardial infarction	
Symptomatic congestive heart failure w/ response to specific treatment	
Intermittent claudication, peripheral arterial bypass for insufficiency,	
gangrene, acute arterial insufficiency, untreated aneurysm ( $\geq$ 6cm)	
History of TIA, or CVA with no or minor sequelae	
Chronic cognitive deficit	
Symptomatic dyspnoea due to chronic respiratory conditions (inc.	
asthma)	
SLE, polymyositis, polymyalgia rheumatic, moderate to severe	
rheumatoid arthritis	
Patients who have required treatment for peptic ulcer disease	
Cirrhosis without portal hypertension, chronic hepatitis	
Diabetes with medication	
Retinopathy, neuropathy, nephropathy	
Hemiplegia or paraplegia	
Creatinine>265umol/L, dialysis, transplantation, uraemic syndrome	
Initially treated in the last 5 years exclude non-melanomatous skin	
cancers and in situ cervical carcinoma	
CML, CLL, AML, ALL, PV	
Non-Hodgkin's Lymphoma, Hodgkin's, Waldenstrồm, multiple myeloma	
Cirrhosis with portal hypertension +/- variceal bleeding	
Metastatic solid tumour	
AIDS & AIDS-related complex	

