#### Variables collected

The following clinical parameters will be collected for NOLAP population: age; sex; place of residence (home with no carers, home with carers, intermediate care, residential home, nursing home); ASA (American Society of Anaesthesiologists); surgical diagnosis (pre-operatively); NELA score; Clinical Frailty Score (Rockwood, 1 to 7); co-morbidities (Charlson; total number of co-morbidities); polypharmacy (5+ medications: yes/no) CT performed within 48 hours of decision (yes/ no); CT

diagnosis; date of assessment for laparotomy, time of day and location (most relevant according to the following list: general surgical ward; other surgical ward; orthopaedics; gynaecology; geriatrics; acute medical ward; other medical ward). Preoperative (within 8 hours of surgical decision) blood markers will also be recorded: lactate; C reactive protein; creatinine and WCC. The actual procedure performed will be recorded for the ELAP patients only.

For comparison to ELAP. This data will be retrieved directly from NELA and ELLSA databases with no extra data required by each participating site.

Remaining variables: length of hospital stay; length of critical care stay (ICU and HDU combined). Both groups will then be followed up for: 30-day complications (Clavien-Dindo Grading); date of discharge; discharge destination (home with no carers, home with carers, intermediate care; residential home, nursing home); 30-day and 90-day mortality and death at 1 year. Actual date of death and cause of death (1a on death certificate) will be recorded.

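### The Q4 comorbidity form does not reliably capture the Charlson index: two defined conditions have no tick box, and the marking rule is at odds with definitions that set severity or time limits

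*Protocol*

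**What the plan says.** Under Variables collected, the protocol lists among the NoLAP variables "co-morbidities (Charlson; total number of co-morbidities". The Definitions section for Q4 says: "These are comorbidities as defined by the Charlson Comorbidity Index". It then gives the marking rule: "Each should be marked as present if there is any previous documented history of each diagnosis". The definitions follow, one per condition.

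Several definitions carry limits. The renal entry reads "Creatinine>265umol/L, dialysis, transplantation, uraemic syndrome" and the solid tumour entry begins "Initially treated in the last 5 years exclude non-melanomatous skin". Two entries matter for a different reason: "SLE, polymyositis, polymyalgia rheumatic, moderate to severe" (continuing to rheumatoid arthritis) and "Patients who have required treatment for peptic ulcer disease".

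Appendix B, Q4, is the form that sites complete. It is a list of short labels with Y/N, for example "Hemiplegia Y/N CKD Y/N", ending with a free-text Other line.

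The Data analysis section lists comorbidities among the baseline characteristics to be described. The 90-day mortality model is adjusted for age, sex and frailty status only.

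**The concern.** The form and its definitions page should describe the same set of conditions and the same threshold for a tick. They appear to differ in two ways: conditions are defined that the form never asks about, and the marking rule seems to accept histories that the definitions would exclude.

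The primary outcome is to characterise the NoLAP population, and comorbidity is one of the characteristics reported. If two Charlson conditions are captured only when someone thinks to write them in, and others depend on which line of the instructions a site follows, the comorbidity profile will partly reflect how sites fill in the form. Appendix A also lists advanced comorbidity as a reason for not operating, so readers will look at this profile when interpreting the decisions.

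**Working it through.** No power or precision figure is involved. The check is a one-to-one match of the boxes in Appendix B, Q4, to the entries under Definitions, Q4, followed by a reading of each definition against the marking rule. The definitions table seems to have lost its label column when the text was read, but each entry can be identified from its wording.

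**Step 1. Count.**

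- Boxes: CCF, COPD, CVA, dementia, hemiplegia, CKD, leukaemia, complicated diabetes, lymphoma, uncomplicated diabetes, mild liver disease, IHD, severe liver disease, PVD, solid tumour, metastatic tumour, AIDS. Total 17.
- Definitions: one entry matching each of those 17, plus connective tissue disease and peptic ulcer disease. Total 19.
- 19 − 17 = 2 definitions without a box. Every box has a matching definition.

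The box list runs through to AIDS and then the Other line, so it reads as complete. The gap does not look like a fault of text extraction.

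**Step 2. Labels and marking rule against definitions.**

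| Box on the form | What the definition requires | Ticked on any documented history? |
|---|---|---|
| CKD | Creatinine above 265 umol/L, dialysis, transplant or uraemic syndrome | Milder documented CKD would also be ticked |
| Solid tumour | First treated within 5 years, some cancers excluded | An older cancer would also be ticked |
| Uncomplicated diabetes | On medication | Diabetes without medication would also be ticked |
| PVD | Where it rests on an aneurysm: untreated and at least 6 cm | A smaller or repaired aneurysm could also be ticked |
| IHD | Documented myocardial infarction | Angina without infarction would also be ticked |

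**Step 3. What one patient looks like under each reading.**

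- Mild documented CKD plus bowel cancer treated 12 years ago. Any documented history: 2 conditions. Definitions applied: 0.
- Treated peptic ulcer plus moderate to severe rheumatoid arthritis, with nothing written on the Other line. Defined conditions present: 2. Boxes ticked: 0.

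These are counts of conditions. The documents give no Charlson weights, so no points are attached.

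**Step 4. Can the analysis repair it?** The form records no date of cancer treatment, no CKD stage, no aneurysm size and no separate item for past infarction. The only creatinine (Q11a) is taken within 8 hours of the decision in an acutely ill patient, so it cannot establish chronic disease. A blank Other line does not separate a condition that is absent from one that was not asked about.

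**Step 5. Do the quality checks catch it?** Validation covers 25% of fields in 10% of cases: 0.25 × 0.10 = 0.025, or 2.5% of all entries. It names key demographic and outcome data. Even where Q4 is checked, a tick that is correct on one reading would pass.

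**The case against.** The strongest case on the other side has five parts.

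- **The Other line.** A reader might infer that the form cannot yield the Charlson index at all. The documents do not support that. A site can write in rheumatoid arthritis or treated ulcer disease, and the definitions page mentions both. What remains is that capture is unprompted and likely to be incomplete.
- **The marking rule.** It follows directly on the sentence tying the items to Charlson definitions. It can be read as setting the standard of evidence (documented, past or present), with the entries below setting what counts. On that reading nothing conflicts, so certain mis-scoring is not shown. The ambiguity stands: the box shows only a short label, both readings are reasonable, and sites may differ.
- **Paired boxes.** A reader might infer that mild and severe liver disease, the two diabetes boxes, or solid and metastatic tumour will be counted twice. Both members of each pair are recorded, so an analyst can collapse them. How the total is derived can be left to the statistical analysis plan.
- **Impact.** Comorbidity is not a covariate in the mortality model and is not among the prognostic markers named in the Aims. The presenting diagnosis is recorded separately (Q11, Q13), so only past ulcer history is affected. This is right, and it limits the point to description.
- **Training.** The protocol promises online training on completing the proforma. This may help, but it would teach the same form, and nothing in the protocol says which reading it will adopt.

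**Conclusion.** The point holds as a form defect of modest reach. Two of the 19 defined Charlson conditions have no prompted box and are likely to be under-recorded. For renal disease, solid tumour, diabetes, aneurysm and ischaemic heart disease, the marking rule or the label is wider than the definition. The same patient may then be scored differently at different sites, and the data collected cannot put that right.

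The consequence falls on the descriptive characterisation of the cohort, not on the adjusted mortality comparison. The missing boxes push recorded comorbidity down and the wide reading pushes it up. They act on different patients and need not cancel, so the net direction is unknown.

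It is tempting to turn this into a shift in the mean Charlson score. That would need weights, the prevalence of milder CKD and the share of sites taking the wide reading. The documents give none of these, so no size is claimed. The conclusion rests on the box list being complete as shown and on the definitions being identifiable without their lost labels.

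**What to change.** 1. Add two Y/N boxes to Appendix B, Q4: connective tissue disease and peptic ulcer disease. The form then has 17 + 2 = 19 boxes for 19 definitions, and a 'no' becomes a recorded answer.
2. Replace the marking instruction under Definitions, Q4, with: mark as present only if the definition below is met.
3. Align the IHD box with its definition, which is myocardial infarction.

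Cost: an edit to one form item, one label and one sentence, with matching fields in REDCap, before data entry opens. Added time per patient at sites is negligible. If entry has already begun, sites would have to revisit Q4 for the patients already entered, because the stored fields do not allow the answers to be reconstructed.

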# **Q8.** Rockwood Frailty Score

1 – Very fit	Robust, active, energetic, well motivated and fit; these people commonly exercise
	regularly and are in the most fit group for their age.
2 – Well	Without active disease, but less fit than people in category 1.
3 – Well, with treated comorbid	Disease symptoms are well controlled compared with those in category 4.
disease	
4 – Apparently vulnerable	Although not frankly dependent, these people commonly complain of being
	"slowed up" or have disease symptoms.
5 – Mildly frail	With limited dependence on others for instrumental activities of daily living.
6 – Moderately frail	Help is needed with both instrumental and non-instrumental activities of daily
	living.
7 – Severely frail	Dependent on others for activities of daily living, or terminally ill.

# Q21a. Clavien-Dindo Classification of Surgical Complications

Clavien-Dindo Classification of Surgical Complications	
Grade I	Any deviation from the normal postoperative course without the need for pharmacological treatment or surgical, endoscopic, and radiological interventions. Allowed therapeutic regimens are: drugs such as antiemetics, antipyretics, analgetics, diuretics, electrolytes, and physiotherapy. This grade also includes wound infections opened at the bedside.
Grade II	Requiring pharmacological treatment with drugs other than allowed for grade I complications. Blood transfusions and total parenteral nutrition are also included.
Grade IIIa	Surgical, endoscopic, or radiological intervention that is not under general anesthesia
Grade IIIb	Surgical, endoscopic, or radiological intervention that is under general anesthesia
Grade IVa	Life-threatening complication requiring intermediate care or intensive care unit management, single organ dysfunction (including dialysis, brain hemorrhage, ischemic stroke, and subarrachnoidal bleeding)
Grade IVb	Life-threatening complication requiring intermediate care or intensive care unit management, multi-organ dysfunction (including dialysis)
Grade V	Death of a patient
Suffix "d"	If the patient suffers from a complication at the time of discharge, the suffix "d" (for "disability") is added to the respective grade of complication. This label indicates the need for a follow-up to fully evaluate the complication

